#### **10.3.9. Durometry**

A durometer is a handheld device that can measure skin firmness or hardness. Durometric examination will be performed using a thin clear plastic (such as Saran wrap or thin report cover/page divider) to identify at least 3 anatomic markers and alignment around the target lesion(s). The approximate center of the lesion should be identified and marked on this template, and the durometer should be centered over this area, with gentle pressure and complete contact, and a series of at least 3 readings should be obtained and recorded. If there are outlying readings, this should be repeated until 3 readings are reasonably concurrent, and these should be recorded. An average score will be calculated for each target lesion. The template used to identify the lesion and the center for readings should be retained for use at subsequent visits. The template may also be used to mark injection points.

### **10.3.10. LoSCAT**

The Localized Scleroderma Assessment Tool (LoSCAT) ([Appendix 3](#)) should be completed by the Investigator to capture disease activity parameters. The LoSCAT is used to classify patients with morphea by disease severity and to identify clinically significant improvement in activity.

Mild, moderate and severe activity corresponds with LoSCAT activity index (LoSAI ) scores of 0–4, 5–12 and 13 and over, and with Physician's Global Assessment of activity (PGA -A) scores of 0–10, 11–30 and 31 and over. Mild, moderate and severe damage corresponds with LoSCAT damage index (LoSDI ) scores of 0–10, 11–15 and 16 and over, and with PGA of damage (PGA -D) scores of 0–18, 19–30 and 31 and over. ([Teske, 2020](#))

Scores for each site will be based on the most severe score for each parameter.

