### **Secondary Objective**

The secondary objective of this study is to evaluate the antifibrotic effects of FCX-013 plus veledimex via durometry and the LoSCAT (Localized Scleroderma Assessment Tool).

**Safety evaluations** include assessment of treatment-emergent adverse events (TEAEs), including serious adverse events (SAEs); change in clinical laboratory values; change in vital signs; change in electrocardiograms (ECGs); and incidence of replication-competent lentivirus (RCL) antibodies.

**Efficacy endpoints** include the change from Baseline in the durometer score and LoSCAT score.

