### **8.1. Subject Inclusion Criteria**

A subject must meet all of the following criteria to be eligible for treatment in this study:

1. Subject is an adult,  $\geq 18$  years of age at Screening, with moderate to severe localized scleroderma/morphea with sclerotic lesions which have been unresponsive to standard of care therapy.
2. Subject has stable control of localized disease (clinically inactive) over the 3 months prior to Screening and through Baseline (Day 1).
3. Subject has not participated in previous clinical research study in the 3 months prior to Screening and through Baseline (Day 1).
4. Subject has provided informed written consent.
5. Female subjects of childbearing potential and male subjects engaging in sexual activity that could lead to pregnancy agree to use of at least one of the following adequate birth control regimens while in the study and for 3 months after study medication (FCX-013 or veledimex) is administered:
  - Male partner with vasectomy
  - Male condom AND partner use of one of the contraceptive options below:
    - Spermicide
    - Intrauterine device or intrauterine system
    - Oral contraceptive, either combined or progestogen alone
    - Contraceptive subdermal implant (e.g., Norplant®)
    - Injectable progestogen (e.g., Depo-Provera®)
    - Contraceptive vaginal ring (e.g., NuvaRing®)
    - Transdermal contraceptive patches (e.g., Ortho Evra®)
  - Subjects of childbearing potential who are abstinent agree to use one of the birth control regimens listed if they initiate sexual activity that could lead to pregnancy during the study.

Periodic abstinence e.g., calendar, ovulation, sympto-thermal, post-ovulation methods and withdrawal are not acceptable methods of contraception.

Non-childbearing potential females are defined as females who are premenarchal, or postmenopausal (12 months with no menstrual period without an alternative medical cause), or who have undergone a hysterectomy, bilateral tubal ligation, bilateral oophorectomy (removal of the ovaries), or hysteroscopic sterilization. Documented verbal history from the subject is acceptable.

6. Subject is, in the opinion of the Investigator, able to understand the study, cooperate with the study procedures and willing to return to the clinic for the required follow-up visits.

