### 9.2. Investigational Product Dosing

#### FCX-013

Subjects will receive intradermal injections of FCX-013 to treatment lesion(s) in a single treatment session, on Day 1.

[Table 2](#) provides details regarding the number of cells, vials and injections per treatment session.

A treatment session of FCX-013 will consist of a maximum of 4 mL of FCX-013 administered in up to sixteen (16) 0.25 mL intradermal injections. The injections will be administered around the perimeter of the sclerotic target lesion(s), approximately 1 cm apart. The Investigator will attempt to administer the full 4 mL of FCX-013. Additional details of FCX-013 administration can be found in [Appendix 2](#).

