### APPENDIX 3. LOCAL SCLERODERMA CUTANEOUS ASSESSMENT TOOL (LOSCAT)

LoSCAT Localized Scleroderma Cutaneous Assessment Tool	LoSAI (Localized Scleroderma Skin Activity Index)			LoSDI (Localized Scleroderma Skin Damage Index)			
	New/Enlarged (past month)  0 = none 3 = N / E	Erythema  0 = none 1 = pink 2 = red 3 = dark red Molaceous	Induration (skin swelling at EDGE)  0 = none 1 = mild 2 = moderate 3 = marked	Dermal atrophy  0 = none 1 = shiny 2 = visible vessels 3 = cliff drop	Sub Q / Deep atrophy  0 = none 1 = flat 2 = concave 3 = marked	Dyspigmentation (hyper or hypo)  0 = none 1 = mild 2 = moderate 3 = marked	Skin Thickness (at CENTER)  0 = none 1 = mild 2 = moderate 3 = marked
Scalp/Face							
Neck							
Chest							
Abdomen							
Upper Back							
Lower Back							
R T	Arm						
	Forearm						
	Hand						
	Thigh						
	Leg						
	Foot						
L T	Arm						
	Forearm						
	Hand						
	Thigh						
	Leg						
	Foot						

LoSAI \_\_\_\_\_ LoSDI \_\_\_\_\_

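### LoSCAT, injection mapping and control-skin measurement are set up so that treated-lesion information can go unrecorded, and a later SAP could not restore it

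*Protocol*

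**What the plan says.** Section 6 of the protocol states that the efficacy endpoints "include the change from Baseline in the durometer score and LoSCAT score". No other efficacy endpoint is named for the antifibrotic objective.

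**LoSCAT.** Section 10.3.10 gives the scoring rule: "Scores for each site will be based on the most severe score for each parameter". The form in Appendix 3 has 18 body-site rows and seven items scored 0 to 3, among them skin thickness at the lesion centre. No row or field is set aside for the treated lesion. Section 9.3 allows up to three candidate lesions and does not require a treated lesion to be the only one in its body site.

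**Injection site and durometry point.** Section 9.2 says "The injections will be administered around the perimeter of the sclerotic target lesion(s), approximately 1 cm apart" and refers to Appendix 2 for details. Section 11.1.1 places the injections in and across the sclerotic area and does not mention the perimeter. Appendix 2 (steps 3 and 11) combines the two. On durometry, Section 10.3.9 says "The approximate center of the lesion should be identified and marked on this template, and the durometer should be centered over this area". The template is to be kept for later visits, but for the injections the wording is only "The template may also be used to mark injection points".

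**Control skin.** Section 9.3 calls for a comparison measurement on healthy skin in the same body region, usually on the opposite side. Section 10.3.9 describes target lesions only. Table 4 has one durometry row without a control entry, and Section 13.5 does not mention a control.

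**Re-reading.** Section 10.3.9 adds: "If there are outlying readings, this should be repeated until 3 readings are reasonably concurrent, and these should be recorded". Section 7.4 confirms that the study is open-label.

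**The concern.** The product is injected into chosen lesions, so the antifibrotic question is what happens in those lesions. LoSCAT answers at body-site level and takes the worst lesion there, so an untreated neighbour can cover the treated lesion's improvement. Durometry is lesion-specific, but its meaning depends on whether the point measured lies in injected tissue. The protocol describes the injection pattern in differing ways and does not require a lasting record of it. The healthy-skin reading is the only within-subject reference in a single-arm study, and it has no visits or number of readings attached.

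All of these concern what is written down at the visit. An SAP can choose how to summarise collected data. It cannot supply a lesion score, an injection map or a control reading that nobody recorded.

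**Working it through.** The protocol gives no figure on this point, so there is nothing to reproduce. The checks below follow from its rules.

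**1. Masking under the worst-lesion rule.** Let T0 and T1 be the treated lesion's skin-thickness score at baseline and later, and U the highest score of any untreated lesion in the same body site, assumed unchanged. Then

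recorded fall = max(T0, U) − max(T1, U).

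For full clearance of the treated lesion (T0 = 3, T1 = 0):

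| U | Site score, baseline → later | Recorded fall | True fall |
|---|---|---|---|
| 0 or no other lesion | 3 → 0 | 3 | 3 |
| 1 | 3 → 1 | 2 | 3 |
| 2 | 3 → 2 | 1 | 3 |
| 3 | 3 → 3 | 0 | 3 |

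In general:
- if U is at or above T0, the improvement is fully hidden;
- if U lies between T1 and T0, it is partly hidden;
- if U is at or below T1, or there is no other lesion, nothing is lost.

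The protocol gives no information on how often subjects have a second lesion in the treated site, so no frequency can be stated.

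**2. Injection passages side by side.**

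| Place | Location given |
|---|---|
| Section 9.2 | perimeter (refers to Appendix 2) |
| Section 11.1.1 | in and across the sclerotic area |
| Appendix 2, steps 3 and 11 | perimeter, and across the fibrotic area |

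Appendix 2 step 3 has the points marked on the skin, and those marks do not last. Step 12 asks for seepage, problems and notes, not positions. The retained template is the natural lasting map, and marking it is optional.

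**3. How far apart could the injection and the reading be?** Assume that injection is at the perimeter only, that the 16 linear cm of Section 9.3 is the total perimeter, and that k equal circular lesions are treated. The distance from centre to perimeter is r = (16/k)/(2π):
- k = 1: 16/6.283 = 2.5 cm
- k = 2: 8/6.283 = 1.3 cm
- k = 3: 5.33/6.283 = 0.85 cm

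A needle track pointing inward would shorten this by up to 1 cm. If injections also cross the lesion, the centre may itself be injected. The wording difference therefore bears on what a centre reading means.

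**4. Control reading.** Section 9.3 requires it. Section 10.3.9 averages readings per target lesion, and the single durometry row in Table 4 covers Baseline and Weeks 4, 12, 26 and 52 (5 visits). Neither says at which of these visits, or with how many readings, the control area is measured. Section 9.3 does not name the instrument; durometry is an inference.

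**The case against.** Durometry already gives an average for each target lesion, so a lesion-level readout exists, and LoSCAT is the body-site instrument beside it. That stands: the missing treated-lesion score is a LoSCAT gap only. Where the treated lesion is alone in its site, an SAP can take that site's skin-thickness item from the form. That also stands, and it limits the problem to subjects with a second lesion in the treated site.

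On injections, Section 9.2 does not say perimeter only, and it refers to Appendix 2, which combines both patterns. The texts can therefore be reconciled. As written they still differ, and Section 11.1.1 omits the perimeter. The 16 cm can also be read as lesion size or as injected length, so the distances above are illustrations. Section 14.7.1 requires administration records, and a procedures manual or case report form not shown here may capture positions or control readings. Sections 10.3.9 and 10.3.10 do not refer to either one, so the protocol does not secure this.

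On control skin, Table 4 lists assessments and does not itemise measured sites, and leaving the control out of Section 13.5 is a matter an SAP could settle. What remains is that the measurement procedure does not carry it.

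A reader might infer that the re-reading rule biases durometry. The documents do not support that. Section 10.3.9 also has the initial series of at least three readings recorded, and a rule applied even-handedly does not shift the expected average. The rule simply has no tolerance and no cap, in an open-label study, and the text does not make clear that every repeated reading is kept.

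**Conclusion.** The point holds in a limited form. LoSCAT can hide part or all of a treated lesion's improvement, up to the full 3 points of the skin-thickness item, but only where an untreated lesion in the same body site scores above the treated lesion's final score. How often this occurs is unknown. Whether the durometry point was injected may go unrecorded; under the stated assumptions it lies about 0.85 to 2.5 cm inside the perimeter. The control reading is required but not placed in the procedure or the schedule.

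Three stronger conclusions are tempting and are not supported:
- That LoSCAT cannot show a treatment effect. It can, wherever no such neighbouring lesion exists.
- That a 3-point change is trivial against the form's full range. Section 10.3.10 starts severe damage at a LoSDI of 16, so 3 points can matter.
- That durometry measures uninjected skin. Appendix 2 includes injections across the lesion.

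Efficacy is secondary and descriptive in about 10 subjects, and Section 13.1 makes no formal sample size determination. No test, power or error rate is affected, and neither is the primary safety objective. What suffers is the interpretability of the antifibrotic readout. The changes are cheap and worth making before data are collected.

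**What to change.** 1. In Section 10.3.10, record the 0 to 3 skin-thickness item for each treated lesion at every LoSCAT visit from Baseline, beside the standard LoSCAT. Cost: 5 visits × 1 to 3 lesions = 5 to 15 extra scores per subject.
2. Reconcile Section 9.2, Section 11.1.1 and Appendix 2 on injection location (no pattern is recommended here), and make marking the injection points on the retained template mandatory on Day 1. Cost: one marking per treated lesion.
3. Write the control-skin reading into Section 10.3.9 and Table 4 at each durometry visit, with the same number of readings as a lesion, name the instrument, and report the result descriptively beside the lesion change. Cost: with the minimum of 3 readings, 3 × 5 = 15 per control area over the study, or 45 if three lesions each have their own area. Section 9.3 already calls for this measurement, so not all of these are additional.
4. State in Section 10.3.9 that every durometer reading, including repeated ones, is recorded and kept.

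The overall downside is a few more non-invasive scores and readings per visit.

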### **10.3.11. SkinDex**

The SkinDex 29+3 ([Appendix 4](#)) is a skin-specific quality of life questionnaire which assesses three subscales: emotions, symptoms, and functioning in the month preceding administration. A fourth subscale was added to characterize morphea-specific concerns: (1) activity limitation as a result of disease, (2) concern for involvement of internal organs and (3) feelings of isolation. ([Klimas, 2015](#))

The SkinDex 29+3 will be administered by providing the questionnaire to the subject, who will be instructed to respond to each question. Study staff will review the questionnaire upon completion and will return it to the subject and ask that they respond to any incomplete lines. The responses will be summed at each applicable timepoint.

## **11. STUDY DRUG MATERIALS AND MANAGEMENT**

### **11.1. Study Drug Materials and Administration**

#### **11.1.1. FCX-013**

FCX-013 will be manufactured from one set of three 3-4 mm biopsies obtained at the Screening Visit. Upon receipt of the biopsies at Fibrocell, FCX-013 will be manufactured by gene modification and expansion of dermal fibroblasts obtained from the biopsy. The tissue will be digested with enzymes to release the fibroblasts, which will then be seeded into a tissue culture vessel. The cells will be expanded, transduced with INXN-2005 (a lentiviral vector encoding the functional MMP-1 gene), and expanded further. If the manufacturing process does not yield an FCX-013 cell count sufficient for at least one administration, or does not meet manufacturing release specifications, an additional set of biopsies may be requested from the subject.

This IP will be provided to the Investigative Site as an opaque cell suspension in 2.0 mL cryovials containing approximately 1.2 mL of FCX-013 with a recoverable volume of 1.0 mL per vial.

#### **Packaging and Labeling**

Up to five (5) vials of FCX-013 will be provided per subject, per treatment session. The vials will be labeled with a minimum of the subject number and the date of manufacture. The secondary container in which the vials are shipped will include the following information:

- IP Name: FCX-013
- Lot Number
- Fill Date and Time
- Expiration Date and Time
- Nominal Conc./Vol.: 10-30 million cells/mL in 1.0 mL
- Manufactured by Fibrocell Technologies Inc. Exton, PA
- CAUTION: NEW DRUG – Limited by US Federal Law to Investigational Use
- NOT EVALUATED FOR INFECTIOUS SUBSTANCES

The cells will be transported to the investigative site as a suspension and the vial will be packaged in a temperature controlled and monitored shipper and delivered by overnight courier.

#### **Storage**

After receipt of the shipped vials, they must be kept sealed in the shipper until ready for use. The Investigator will be responsible for accurate, written records of all FCX-013 received. The Sponsor or designee will be permitted upon request to audit the administration procedures and records.

FCX-013 Drug Product will be shipped same day or overnight delivery to the clinic and must be administered within 40 hours of the fill time as indicated on the label.

### Preparation and Administration

One administration of FCX-013 is up to 4 mL of cell suspension administered in up to sixteen (16) 0.25 mL intradermal injections.

The maximum dose of FCX-013 will be determined by characteristics of the lesion(s) chosen. Approximately 100 million cells will be administered at each dose administration. One administration of FCX-013 will consist of a maximum of 4 mL of FCX-013 administered in up to sixteen (16) 0.25 mL intradermal injections. The injections will be administered in and across the sclerotic area of target lesion(s). The Investigator will attempt to administer all 4mL of FCX-013. This will be accomplished by selecting target lesions that are as close as possible to 16 linear cm.

Table 5 provides details regarding the number of cells, vials and injections per administration.

**Table 5: FCX-013 Cell Count and Injections per Administration**

FCX-013 Cells	~100 million
Concentration of FCX-013 Suspension	10-30 million cells/mL
# Vials	Up to 5
Injections per Vial	1
Cells per Injection	6 million
Number of Injections	Up to 16

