**Table 2: FCX-013 Cell Count, Vial and Injections per Treatment Session**

FCX-013 Cells:	~100 million
Concentration of FCX-013 Suspension:	10 to 30 million cells/mL
# Vials:	Up to 5
Cells per Injection:	6 million
Number of Injections:	Up to 16 (each injection 0.25mL)

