## **APPENDIX 2. INVESTIGATIONAL PRODUCT ADMINISTRATION INSTRUCTIONS**

1. The FCX-013 injections are to be administered by the PI or an appropriately trained, qualified, and delegated Sub-I.
2. Administer anesthesia. Subjects will be administered anesthesia per standard of care at the Investigative Site. To minimize pain and discomfort during the IP administration, the PI or delegated sub-I should determine the most appropriate anesthetic for each subject, including the use of topical anesthetic cream, local anesthesia, conscious (moderate) sedation, or a combination thereof. In addition, medication could be considered during and after the injections to treat pain and/or anxiety (e.g., lorazepam).
3. Mark the lesional skin to indicate injection points, approximately 1 cm apart, around the perimeter of the lesion and across the fibrotic area.
4. Approximately 15 minutes prior to the administration of FCX-013, remove the subject's treatment vials from the shipper.
5. Resuspend the cells by gently inverting the injection vial three times.
6. Tap the top of each vial to release any fluid in the cap prior to opening the vials. Do not dilute the product.
7. Unscrew the cap and, using a detachable bore (21-gauge needle), aseptically draw 1.0 mL from one vial.
8. Once the product is in the syringe, remove the 21-gauge needle and replace it with a larger-gauge needle for injection of the product (e.g. – 25 or 27 gauge). Do not use a 21-gauge needle for injection of the product. Follow sterile technique during this process. Note: Living cells are fragile and should be handled gently, especially when being aspirated into a syringe. Go slowly and use care during this process.
9. Hold the syringe using the proper technique: the bevel facing upwards and the arms of the syringe are vertical. Some clinicians may prefer to bend the needle upwards at about a 15-degree angle to facilitate staying in a superficial plane — but use of this technique is optional. Grip the syringe with the middle and index finger below the arms, placing the thumb on the upper arm. Do not place the thumb on the plunger while directing the needle into the skin to avoid premature discharge of the product.
10. Insert the 25 or 27-gauge needle at the first mark, into or beneath the dermis, at the fibrotic area. The graduated markings on the syringe should be visible to ensure that the correct amount is being injected.

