11. Slowly inject FCX-013 0.25 mL per linear centimeter, with light pressure on the plunger, injecting very tiny boluses (the cells must be injected as delicately as possible) into the treatment area as the needle is withdrawn (retro-tracing). The injections should be performed intradermally, at the perimeter of the lesion and across and into the fibrotic area. Stop injecting before withdrawing the needle and remove your thumb from the plunger.
12. Record any seepage of product or other issues or notes regarding the procedure.

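### Table 5's one injection per vial from up to five vials cannot give its own up to 16 injections or about 100 million cells; the lower half of the stated concentration range also falls short of that cell count

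*Protocol*

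**What the plan says.** Section 11.1.1, Preparation and Administration, sets a 4 mL ceiling, "administered in up to sixteen (16) 0.25 mL intradermal injections". It gives approximately 100 million cells as the amount administered, and refers the reader to Table 5 for cells, vials and injections.

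Table 5 lists about 100 million cells, 10 to 30 million cells/mL, up to 5 vials, 6 million cells per injection and up to 16 injections. It also has the row "Injections per Vial 1".

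Table 2 (Section 9.2) gives the same cell total, concentration range, vial count and cells per injection, and states the injections as "Up to 16 (each injection 0.25mL)". It has no injections-per-vial row.

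On volume per vial, Section 11.1.1 describes cryovials "with a recoverable volume of 1.0 mL per vial", and the label text reads "Nominal Conc./Vol.: 10-30 million cells/mL in 1.0 mL". Appendix 2 tells the injector to "aseptically draw 1.0 mL from one vial", and adds "Do not dilute the product" and "Slowly inject FCX-013 0.25 mL per linear centimeter".

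**The concern.** The rows of a dosing table should multiply out to its own totals, and Table 5's do not. Vials times injections per vial falls far short of the injection count, and so of the cell count. The row also disagrees with the volumes given in Section 11.1.1 and Appendix 2.

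A second mismatch is milder. Both tables give one figure for cells per injection and one approximate total, beside a threefold concentration range. With injection volume and total volume fixed and dilution not allowed, cell count must move with concentration, so single figures can describe only part of that range.

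The primary objective is safety and the product is a gene-modified cell suspension. Table 5 is the place to which the text sends the reader for the quantities given, so it should agree with itself and with the administration instructions.

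**Working it through.** **Inputs**
- Vials: up to 5 (Tables 2 and 5; Section 11.1.1, Packaging and Labeling)
- Injections per vial: 1 (Table 5 only)
- Cells per injection: 6 million (Tables 2 and 5)
- Injections: up to 16 (Tables 2 and 5; Section 11.1.1)
- Volume per injection 0.25 mL, maximum 4 mL (Sections 9.2 and 11.1.1)
- Volume per vial: 1.0 mL (Section 11.1.1; Appendix 2, step 7)
- Concentration: 10 to 30 million cells/mL (Tables 2 and 5; label text)

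**The plan's own total, leaving out the per-vial row**
- 16 × 0.25 mL = 4 mL, as stated.
- 16 × 6 million = 96 million, which is 4% below 100 million and fair for an approximate figure.

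The other rows therefore agree with one another, and the conflict arises from the per-vial row.

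**Table 5 with the per-vial row**
- Injections = vials × injections per vial = 5 × 1 = 5, against up to 16.
- Volume = 5 × 0.25 mL = 1.25 mL, against 4 mL.
- Cells = 5 × 6 million = 30 million, against about 100 million.
- In reverse, 16 ÷ 1 = 16 vials, against up to 5.
- From the volumes, 1.0 mL ÷ 0.25 mL = 4 injection volumes per vial, against 1.

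**Could an injection in that row mean one 1.0 mL draw?** Five draws are still not 16 injections. Also, 6 million cells in 1.0 mL is 6 million/mL, below the stated range. That reading fails too.

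**Cell counts against concentration**
- Concentration implied by the tables: 6 million ÷ 0.25 mL = 24 million/mL.
- Concentration implied by 100 million in 4 mL: 100 ÷ 4 = 25 million/mL.

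| Million cells/mL | Million per 0.25 mL | Million in 4 mL |
|---|---|---|
| 10 | 2.5 | 40 |
| 20 | 5.0 | 80 |
| 24 | 6.0 | 96 |
| 25 | 6.25 | 100 |
| 30 | 7.5 | 120 |

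**Could the total mean cells supplied rather than given?** Five vials × 1.0 mL × 20 million/mL = 100 million supplied. But Section 11.1.1 speaks of cells administered and caps the volume at 4 mL, which holds 80 million at that concentration.

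**The case against.** The strongest reply is that the row is an isolated slip with little practical effect. The Synopsis, Section 7.1, Section 9.2, Table 2 and the text of Section 11.1.1 all give up to sixteen 0.25 mL injections. Appendix 2 gives the volume drawn per vial and the volume per linear centimetre. A trained injector following those steps would not stop after one injection from each vial. That stands. A reader might infer from the arithmetic that subjects would receive five injections and 30 million cells; the documents do not support this.

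On the second mismatch, one can reply that the total is marked as approximate, and that 24 to 25 million/mL lies inside the stated range. This also stands in part. A reader might infer a hard floor of 25 million/mL, but the tables' own 96 million corresponds to 24 million/mL, so the limit is soft. Nor is the 100 million figure unqualified: Section 11.1.1 calls it approximate and links the maximum dose to features of the chosen lesions.

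These qualifications do not close the gap. The link is to the lesion and not to lot concentration, and the same section has the investigator try to give all 4 mL. Approximation covers 96 million; it does not reasonably cover 40 to 80 million, which is 60% to 20% below 100 million.

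**Conclusion.** Table 5 is internally inconsistent. Its per-vial row implies 5 injections, 1.25 mL and 30 million cells, against up to 16 injections, 4 mL and about 100 million cells. No reading tried, and no other passage, repairs it. The result rests only on the table's own rows and the 0.25 mL injection volume. The vial count is a maximum, so fewer vials would only widen the gap.

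The second mismatch is real but weaker. The stated cell counts fit about 24 to 25 million/mL, while the full 4 mL holds 40 to 120 million cells across the stated range. The protocol does not say how close approximately must be and gives no distribution of lot concentrations, so no share of subjects falling short can be derived.

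A reader might also infer an effect on the trial's results. The documents do not support that: the analysis sets in Section 13.2 do not use cell count, and no endpoint depends on it. The point is a correction to a reference dosing table, worth making because the text directs readers to that table.

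**What to change.** The sponsor should reconcile two sets of passages:

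1. The injections-per-vial row in Table 5 with the volume per vial and per injection in Section 11.1.1 and in Appendix 2, steps 7 and 11.
2. The cells per injection and total cells in Table 2, Table 5 and Section 11.1.1 with the concentration range in Tables 2 and 5 and the label text.

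This review does not say which passage prevails and proposes no dose, volume or vial count. The cost is amendment wording for one table row and a few sentences, with no new data collection or analysis.
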